### **7.13 Physical Examinations**

Physical examinations should be conducted according to the Schedule of Events (Section 1.2). Full physical examinations should evaluate all major organ systems, including the following categories: general, head, eyes, ears, mouth/throat, neck, heart, lungs, abdomen, lymph nodes, joints, extremities, integumentary, neurologic, and psychiatric. Other examinations may be focused, at the discretion of the Investigator, to identify changes from baseline or evaluate changes based on the patient's clinical symptoms. Weight is to be reported on Day 1 of each cycle, and height at Screening visit only.

### **7.14 Vital Signs**

Vital sign measurement will be recorded according to the Schedule of Events (Section 1.2). Vital signs include pulse rate, respiratory rate, systolic and diastolic blood pressure, oxygen saturation (oxygen saturation at Screening and on dosing days only), and temperature (oral). It is preferred that the same arm be used for all blood pressure readings, if possible. Where feasible, vital signs should be measured before having blood drawn for laboratory evaluations.

The study site must be equipped for medical emergencies and have access to an intensive care unit.

If the patient experiences a Grade > 2 IRR or hypotension on the dosing day, the patient may be monitored overnight at the discretion of the Investigator. Longer periods of monitoring may be implemented at the discretion of the Investigator.

### **7.15 Electrocardiograms**

The Investigator or designee will review all ECG interpretations and interval duration measurements for clinical significance. Any ECG interpretation deemed to be clinically significant will be reported as an AE as described in Section 7.1.

## 7.16 Cardiac Function

An echocardiogram, nuclear scan, or multigated acquisition (MUGA) scan will be performed for all patients as per schedule of assessments, within 60 days prior to dosing and at EOT to assess cardiac function and left ventricular ejection fraction (LVEF). The same assessment method should be used for the same patient throughout the study, if feasible.

## **8.0 ASSESSMENT OF EFFICACY**

### **8.1 Treatment Response Assessment**

Tumor response will be evaluated using RECIST 1.1 criteria ([Eisenhauer, 2009; Appendix 2](#)).

Tumor burden will be characterized prior to enrollment, and response assessments will be performed approximately every 9 weeks starting from C1D1.

### **8.2 Tumor Imaging (Computed Tomography or Magnetic Resonance Imaging)**

Computed tomography (CT) with contrast or magnetic resonance imaging (MRI) (for patients who cannot tolerate CT contrast) will be obtained to document metastatic disease, identify target lesions as described in RECIST 1.1, and to assess response and disease progression. Imaging by CT scan with contrast or MRI will be performed at Screening, and approximately every 9 weeks during the treatment period regardless of cycle number or dose interruption.

Scans taken as part of standard medical practice up to 42 days prior to first dose of study treatment can be used for Screening. During the treatment, scans may be performed at timepoints other than every 9 weeks as clinically indicated to assess tumor progression. A standard-of-care brain MRI occurring prior to the 28-day screening window may be acceptable based on consultation with the Medical Monitor.

The text 'CCI' is displayed in a large, bold, red font, centered on a solid black rectangular background.

At Screening, a brain MRI is only required for patients with a history of brain metastases and should be followed as clinically indicated. Other scans may be included as clinically indicated.

For patients who stop study treatment in the absence of disease progression (eg, due to unexpected toxicity), scans should continue to be collected approximately every 9 weeks until disease progression or initiation of systemic anti-tumor therapy other than the study treatment (whichever is earlier) or unless patient withdraws consent.

The same imaging procedure and specifications (eg, contrast agent, scanner, slice thickness, etc.) used to define measurable target and non-target lesions must be used throughout the study for each patient.

Computed tomography scans may not be performed at sites or in countries where additional radiology approval is required, unless that approval is sought and granted.

The text 'CCI' is displayed in a red font, centered on a solid black rectangular background.

CCI

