#### 4.1.2 Inclusion Criteria for Specific Tumor Types

A patient may be entered into this study only if he/she meets all of the following additional criteria specific to that patient's tumor type:

- Head and Neck Squamous Cell Carcinoma

1. Patients must have histologically or cytologically confirmed advanced, recurrent, or metastatic HNSCC that could not be treated with curative intent. "Advanced" is defined as either locally advanced HNSCC not amenable to curative surgery or radiotherapy or with distant metastases.
2. Patients who have undergone treatment with anti-PD-1 or antibody to programmed death-ligand 1 (anti-PD-L1) (together termed "anti-PD-(L)1") must have had the last dose of antibody at least 4 weeks prior to receiving any study drug and evidence of tumor progression before they can be enrolled into this study.
3. Patients must have known status by pathology for HPV and Epstein-Barr virus (EBV) in HNSCC, either metastatic or recurrent disease.
4. Patients must have experienced progression (or toxicity precluding additional treatment) on any first- or second-line platinum-based chemotherapy and anti-PD-(L)1 antibody, unless they are ineligible for such treatment, **OR**,
5. Patients must be ineligible for platinum-based (either cisplatin or carboplatin) chemotherapy or chemoradiation due to decline in renal function and/or patient's intolerance.

- Colorectal Cancer
  1. Patients must have a histologically or cytologically confirmed diagnosis of advanced CRC; patients in Phase 2 must have confirmed *KRAS* (US) or *RAS* (ex-US) wild type EGFR-expressing advanced CRC. "Advanced" is defined as either locally advanced unresectable cancer or metastatic disease.
  2. Patients must have received at least 2 prior cancer therapy regimens administered for metastatic disease including fluoropyrimidine, irinotecan, and oxaliplatin, unless ineligible or intolerant for such treatment.
  3. Patients with MSI-H or dMMR tumors must have been exposed to checkpoint inhibitors such as anti-PD-1.

A large, bold, red logo consisting of the letters "CCI" in a sans-serif font. The letters are outlined in red and filled with a lighter red color. They are positioned against a solid black rectangular background.

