# CCI

## 4.2 Exclusion Criteria

Patients who meet any of the following criteria are ineligible:

1. Use of an investigational agent or an investigational device within 28 days before administration of first dose of study drug(s)
2. Patients who have an active, known, or suspected autoimmune disease. Patients requiring systemic treatment within the past 3 months or a documented history of clinically severe autoimmune disease that requires systemic corticosteroids or immunosuppressive agents (exceptions include any patient on 10 mg or less of prednisone or equivalent, patients with vitiligo, hypothyroidism stable on hormone replacement, Type I diabetes, chronic graft-versus-host disease, Graves' disease, Hashimoto's disease, alopecia areata, eczema, psoriasis, or with Medical Monitor approval).
3. History of allergy or known hypersensitivity to murine protein or study drug components
4. History of organ transplant that requires ongoing use of immunosuppressive agents
5. Patients who have been previously treated with IL-2 or IL-15

6. Patients with HNSCC who require treatment with anticoagulation therapy are not eligible. Use of warfarin for CRC, **CCI** [REDACTED] patients within 14 days of initiating study drug(s) is not permitted. Additional information about anti-coagulant therapy on treatment can be found in Section [5.10.3](#).
7. Known Grade 3 or 4 hypersensitivity reaction to cetuximab, history of allergy to red meat or tick bites, or history of positive test results for immunoglobulin E antibodies against cetuximab
8. Patient has had prior Grade 4 IRR to cetuximab
9. Unresolved toxicity from previous anti-cancer therapy, unless resolved to Grade  $\leq 1$  or baseline; or resolved to Grade 2 (with the exceptions outlined in the inclusion criteria or deemed clinically not significant, and approved by the Sponsor); or resulting from incomplete recovery from recent surgery (major)
10. Prior surgery or radiotherapy within 14 days of initiating study drug(s). Patients must have recovered from all acute radiation-related toxicities, not require corticosteroids, and have not had radiation pneumonitis.
11. Patients participating in observational studies should be discussed with the Medical Monitor to confirm eligibility.

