12. Patients who have had  $< 28$  days since the last anti-cancer treatment, chemotherapy, or biological therapy, or  $< 14$  days from approved tyrosine kinase inhibitor therapy (sunitinib, sorafenib, vemurafenib, dabrafenib, cobimetinib), or systemic or inhaled steroid therapy at doses greater than 10 mg of prednisone or equivalent before administration of the first dose of study drug(s)
13. Patients who have received systemic interferon alpha (IFN $\alpha$ ) within the previous 6 months prior to enrollment in the study are not eligible.
14. Active infection requiring systemic therapy within 7 days prior to dosing
15. Evidence of clinically significant interstitial lung disease or active, noninfectious pneumonitis
16. Known immunodeficiency or active HIV (antibodies to HIV-1 or HIV-2). However, HIV-associated ASCC patients on effective anti-retroviral therapy with CD4+ count  $\geq 300/\mu\text{L}$  and undetectable viral load are eligible.
17. Known to be seropositive or active for hepatitis B or hepatitis C as defined in Section [5.13.6](#). Patients who had hepatitis B but have received an antiviral treatment and show non-detectable viral DNA for 3 months are eligible. Patients who are seropositive because of hepatitis B virus vaccine are eligible.
18. Prolonged Fridericia's corrected QT interval (QTcF)  $> 450$  ms for men and  $> 470$  ms for women at Screening
19. History of unstable or deteriorating cardiac disease within the previous 6 months prior to Screening including but not limited to the following:

- a. Unstable angina or myocardial infarction
- b. Congestive heart failure (New York Heart Association Class III or IV)
- c. Uncontrolled clinically significant arrhythmias

20. Has a known additional malignancy that is progressing or requires active treatment; exceptions include basal cell carcinoma of the skin, SCC of the skin that has undergone potentially curative therapy, or in situ cervical cancer. An incidental finding of prostate cancer (identified upon resection of the prostate) is acceptable, provided that the following criteria are met: Stage T2N0M0 or lower; Gleason score  $\leq 6$ , and prostate specific antigen below lower limit of normal by local laboratory.

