## 5.2 Study Periods

### 5.2.1 Screening Period

Patients will provide written informed consent to participate in the study before completing any protocol-specified procedures or evaluations not considered to be part of the patient's standard of care. Procedures that were performed for standard of care prior to signing informed consent may be used for screening purposes (eg, full physical examination) as long as the procedures were completed within the window of that assessment during the Screening period (Section 1.2). After signing the informed consent form (ICF), patients will be evaluated for all eligibility criteria during the Screening period before administration of study drug(s). Rescreening after screen failure will be allowed after consultation with the Medical Monitor. The Screening window is 28 days. Baseline scan(s) available up to 14 days prior to signing the ICF are acceptable.

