## 6.6 Definitions

### Run-in period:

Eligible patients on combination therapy will receive cetuximab 400mg/m^2 IV as a loading dose during the study run-in period (Day -7). The run-in period therefore starts from the time the patient receives cetuximab and ends when the patient receives combination treatment of NKTR-255 +cetuximab.

**Study drug or study treatment:** Study drug or study treatment refers to NKTR-255 or cetuximab.

**Study day:** Study Day 1 (C1D1) is the first day that the combination treatment of NKTR-255 +cetuximab begins.

**Baseline:** Unless otherwise specified, the baseline value for each variable is the last non-missing value collected at the time (if collected) closest to, but prior to, the start of NKTR-255 administration. For triplicate ECG data, the record with three non-missing value will be considered as non-missing. If multiple measurements occur on the same day at the same time, or on the same day but the time is not available, the average of the measurements (for continuous data) will be considered the baseline value. When dosing times and/or observation times are not collected, it is assumed that protocol planned in-office assessments obtained on the day of the first dose of study drug are prior to administration of the first dose of study drug and therefore considered baseline values.

**Last known alive date:** The date of last known alive date will be derived for patients unknown to have died or known alive at the analysis cut-off by using following dates:

- Patient assessment dates (blood draws **CCI** [REDACTED], vital signs, performance status, ECG, tumor assessments, ECOG, or tumor biopsy dates)
- Start and end dates of anti-cancer therapies administered after study treatment discontinuation
- AE start or end date
- Concomitant medication start or end dates
- Last date of contact collected on the 'Survival follow-up' eCRF (do not use date of survival follow-up assessment unless status is 'alive')
- Study treatment start or end date
- Date of discontinuation for study participation on disposition eCRF pages (do not use if reason for discontinuation is lost to follow-up)

Only dates associated with actual examinations of the patient will be used in the derivation. Dates associated with a technical operation unrelated to patient status such as the date a blood sample was processed will not be used.

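### The RECIST baseline scan may be up to 42 days old and may predate the last prior anti-cancer treatment, so pre-study tumour change can be scored as on-study response or progression

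*Protocol*

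**What the plan says.** **Age of the baseline scan.** Protocol Section 8.2: "Scans taken as part of standard medical practice up to 42 days prior to first dose of study treatment can be used for Screening". Section 5.2.1 gives a related allowance, "Baseline scan(s) available up to 14 days prior to signing the ICF are acceptable", next to "The Screening window is 28 days".

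**Time since prior treatment (Protocol Section 4.2).** Exclusion 12 bars a patient with fewer than 28 "days since the last anti-cancer treatment, chemotherapy, or biological therapy", or fewer than 14 "days from approved tyrosine kinase inhibitor therapy" (five agents are named), counted to the first dose of study drug. Exclusion 10 bars surgery or radiotherapy within 14 days of starting study drug. For HNSCC patients previously given anti-PD-(L)1, Section 4.1.2 adds that they "must have had the last dose of antibody at least 4 weeks prior to receiving any study drug and evidence of tumor progression". It sets no date for the scan.

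**What counts as first dose.** SAP Section 6.6: "Study drug or study treatment refers to NKTR-255 or cetuximab". In Phase 1b the first dose is therefore the cetuximab load on Day -7.

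**What the scan is used for.** Protocol Appendix 2 defines PR as a fall of at least 30% from baseline in the target-lesion sum. It defines progression as a rise of at least 20% over the smallest recorded sum, with an absolute rise of at least 5 mm. SAP Section 6.6 takes as baseline the latest value before NKTR-255. SAP Section 7.5 requires CR or PR to be confirmed at least 4 weeks later. It drops assessments made after new systemic therapy, or after surgery or radiotherapy on target lesions.

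**The concern.** RECIST attributes to study treatment whatever happens between the baseline scan and the on-study scans. That is reasonable only if no other treatment falls in between. Here the scan limit (42 days) is longer than every washout (28 or 14 days), and the visible text does not require the scan to follow the last prior treatment.

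The error can go either way. Lasting shrinkage from earlier chemotherapy, a kinase inhibitor or radiotherapy would move a patient towards PR. Untreated growth between an old scan and first dose would move a patient towards progression and make PR harder to reach.

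At stake in Phase 1b are the descriptive ORR, BOR, CBR, DOR, PFS and waterfall plots. Under the protocol as written, ORR is also a Phase 2 primary efficacy objective and drives the Bayesian rules in Section 9.2.

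**Working it through.** **1. Reproduce the 42 days.** Table 1 places Screening within 28 days of the first run-in day, which is the first dose. Section 5.2.1 adds 14 days before consent: 28 + 14 = 42, the Section 8.2 figure.

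**2. Treatment that can follow the baseline scan.** Overlap = 42 minus the latest day on which prior treatment is allowed.

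| Prior treatment | Latest allowed (days before first dose) | Overlap |
|---|---|---|
| Chemotherapy, biologics | 28 | 42 - 28 = 14 days |
| Named kinase inhibitors | 14 | 42 - 14 = 28 days |
| Surgery, radiotherapy | 15 (14 if day 14 itself is allowed) | 42 - 15 = 27 days (28) |

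If the scan had to follow the last prior treatment, every overlap would be 0.

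**3. Interval to the first on-study scan.** The oldest baseline is 42 + 7 = 49 days before C1D1. The 9-week scan is then 49 + 63 = 112 days after baseline, or 119 days with the +7-day window.

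**4. Effect on the PR threshold.** If the target sum has already changed by a fraction x between scan and first dose (negative for shrinkage), the further shrinkage needed for PR is 1 - 0.70/(1 + x).

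- x = -10%: 1 - 0.70/0.90 = 22.2%
- x = -20%: 1 - 0.70/0.80 = 12.5%
- x = -30%: 1 - 0.70/0.70 = 0%
- x = +10%: 1 - 0.70/1.10 = 36.4%

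In the last case, further growth of only 1.20/1.10 - 1 = 9.1% reaches the 20% progression threshold, provided the 5 mm condition is met and baseline is the smallest sum. The values of x are illustrative; the documents give none.

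**5. Phase 1b scale.** Assuming 30 evaluable patients (the protocol plans approximately 30 in escalation), one false responder adds 1/30 = 3.3 percentage points to ORR.

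**6. Phase 2 scale, for the protocol as written only.** The prior is Beta(0.25, 0.75); with r responses in n patients the posterior is Beta(0.25 + r, 0.75 + n - r).

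At the initial n = 12:

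- Suspension needs Pr(ORR ≤ 0.10) > 85%. 0/12 gives 0.96 (met); 1/12 gives 0.62 (not met).
- The 30% criterion is on Pr(ORR > 0.25). 2/12 gives 0.21 (not met); 3/12 gives 0.46 (met).

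One misattributed response can reverse either result.

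At a fixed n = 50 with no interim looks, selection as superior needs 16 responses. If a share c of non-responders is misclassified, the apparent ORR is p + (1 - p)c. At true ORR 0.25 the chance of selection is 16.3% for c = 0, 25.1% for c = 2.5%, 35.6% for c = 5% and 58.3% for c = 10%. The range of c is an assumption.

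**The case against.** **Eligibility makes continuing response to prior therapy less likely.** The population is relapsed or refractory. HNSCC patients given anti-PD-(L)1 need evidence of progression, and HNSCC criterion 4 asks for progression or precluding toxicity unless the patient is ineligible for such treatment. This stands as mitigation, but it is partial: the CRC criterion asks for prior regimens without requiring progression, and none of these criteria dates the scan.

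**SAP 7.5 may already catch local treatment.** Take a target sum of 100 mm in which a 50 mm lesion, irradiated between scan and first dose, shrinks to 15 mm. The sum becomes 65 mm, a 35% fall. A reader might infer a certain false PR. Read literally, however, 7.5 drops every scan made after radiotherapy on a target lesion, so this patient would have no usable on-study assessment and no PR. The clause can also be read as covering on-study treatment only, and the SAP does not say which is meant. Under either reading it does not cover prior systemic therapy.

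**Confirmation and the SAP baseline rule.** Confirmation at 4 weeks or more removes transient shrinkage, not lasting shrinkage. A newer pre-dose scan would replace the old one, but none is required when a standard-of-care scan is accepted.

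**Redaction.** Parts of Section 8.2 are blacked out, so the absence of a rule can be asserted only for the visible text.

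**Relevance.** The SAP says only Phase 1b enrolled. Its primary endpoints there are DLTs and TEAEs, and its secondary ORR endpoint names other tumour types. HNSCC and CRC response is descriptive. This limits the consequence but does not remove the gap.

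**Conclusion.** The gap is real and should be closed. A patient who meets every visible criterion can have a RECIST baseline that predates the last prior treatment by up to 14 days (chemotherapy or biologics), 28 days (kinase inhibitors) or about 27 days (surgery or radiotherapy). The result rests on the stated day limits and on first dose being the Day -7 cetuximab load. The figure for surgery and radiotherapy matters for response only if the 7.5 exclusion does not reach treatment given before first dose.

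Three stronger readings are not supported:

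- *Sections 5.2.1 and 8.2 contradict each other.* They share the 42-day outer limit. They differ only when consent is later: consent 7 days before first dose gives 7 + 14 = 21 days under 5.2.1. That is a wording point.
- *ORR is inflated.* The documents show that misattribution is possible, not how often it occurs, and it can run in either direction.
- *A decision was affected.* The Phase 2 ORR rules were not reached, and response does not carry the Phase 1b primary endpoints.

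**What to change.** **Protocol, Sections 8.2 and 5.2.1.** Accept a standard-of-care scan as the RECIST baseline only if it was taken after the last prior anti-cancer therapy and after any surgery or radiotherapy. Otherwise use the Screening tumour assessment already scheduled in Table 1. Use the same wording in both sections, so that the age limit is also clear when consent is later than 28 days before first dose.

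**SAP, for patients already enrolled.** A protocol change cannot help them, so:

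- flag each patient whose baseline scan precedes the end of prior treatment, using the dates needed to check exclusions 10 and 12;
- report ORR and BOR with and without those patients, by tumour type as already planned;
- state in Section 7.5 whether the exclusion covers treatment given between the baseline scan and first dose.

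**Cost.** Some patients would need the scheduled Screening scan instead of an older one. The SAP gains one flag, one repeated summary and one clarifying sentence. No sample size, washout or decision threshold changes.

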## **9.0 STATISTICAL METHODS PLANNED IN THE PROTOCOL AND DETERMINATION OF SAMPLE SIZE**

### **9.1 General Considerations**

In general, continuous data will be summarized by descriptive statistics, including number of patients, mean, standard deviation, median, minimum, and maximum. Categorical data will be summarized by the number and percentage of patients.

A description of analysis methods and detailed definitions for efficacy and safety endpoints will be provided in the statistical analysis plan (SAP). The potential impact of COVID-19 on this trial will be assessed. Any changes to the analyses that are required due to COVID-19 will be detailed in the SAP.

